AVAPS-AE is a mode of therapy (Philips Resironics Inc, Monroeville, Pa) with potential advantages over the currently established modes of non-invasive positive pressure ventilation (CPAP and bilevel therapy). This mode of therapy incorporates AVAPS (automated adjustable IPAP setting to maintain target ventilation with a settable rate of change), Auto EPAP and Auto Back up Rate. We believe that these automated parameters will allow better nocturnal ventilatory control to offset the differing elastic and resistive loads imposed by changes in body position during sleep. Furthermore, AVAPS-AE will counter the changing ventilatory requirements due to alterations in lung volumes and airway resistance during different stages of sleep. In summary, the AVAPS-AE mode will enable automatic adjustment in response to ventilatory changes throughout the night. The device platform used in this study with the AVAPS-AE feature is in the BiPAP A40 platform. This device uses existing modes of therapy, therapy features, and algorithms as that which have been previously cleared by the Food and Drug Administration (FDA) (K121623).

III. Study Objectives/Endpoints

Specific aim #1: Evaluate the effects of novel application of Averaged Volume Assured Pressure Support (AVAPS-AE) therapy on time to (# of days) emergent and non-emergent healthcare utilization in patients with sleep-disordered breathing who are hospitalized with co-morbid COPD.

Specific aim #2: Evaluate the effects of novel application of Averaged Volume Assured Pressure Support (AVAPS-AE) therapy on the number of emergent and non-emergent healthcare utilization over 6 months;

A Pilot, Multi-Center, Randomized, Open-Label, Parallel Group Study to Assess the Effects of a Novel Application of Averaged Volume Assured Pressure Support Ventilation (AVAPS-AE) therapy on Re-hospitalization in Patients with Sleep-Disordered Breathing with co-morbid COPD.

Confidential

costs related to re-hospitalization; number of visits to physician offices or emergency rooms, and health-related quality of life (disease-specific and general HR-QOL measures).

Primary Endpoints

Composite end-point of time to occurrence of emergent healthcare utilization (such as re-hospitalization, unscheduled physician office visits, urgent care visits or emergency room visits).

Secondary Endpoints:

1. Healthcare Costs
2. Change in quality of life (SF-36) at 30 and 60-days
3. Change in quality of life (FOSQ) at 30 and 60-days

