Two different quality of life questionnaires will be used in this study. Quality of life questionnaires are important tools for measuring health status changes in participants receiving an intervention. The general health questionnaire that measures functional health, well-being, and physical and mental health (SF-36) will be used in this study. The disease specific quality of life questionnaire (Functional Outcome of Sleep Questionnaire, FOSQ) will also be used in this study. Participants will be asked to complete these questionnaires prior to discharge.

Randomization

Following the completion of the screening procedures to determine study eligibility, participants will be randomly assigned to one of two study arms: 1) Intervention Group (AVAPS-AE), or 2) Standard of Care (SOC). A randomization website will balance the therapy assignments within each of the three classifications of COPD severity: Gold Stage 2, 3, and 4. The research sites will attempt to balance recruitment between stage-3 and stage-4 patients; however, enrollment of stage-2 patients will be capped at 10, as this severity comprises a small proportion of the hospitalized patients with COPD.

Intervention Group:

AVAPS settings:

• Target Tidal Volume	8 ml/kg of ideal body weight
• Pressure Support Min / Max	4 / 26 cmH ₂ O
• Max Pressure	30 cmH ₂ O
• EPAP Min / EPAP Max	4 / 20 cmH ₂ O
• Rate	Auto

Participants in the intervention group will be sent home the AVAPS-AE therapy device. They will receive one on one training on the device as well as a user manual

SOC Group:

A Pilot, Multi-Center, Randomized, Open-Label, Parallel Group Study to Assess the Effects of a Novel Application of Averaged Volume Assured Pressure Support Ventilation (AVAPS-AE) therapy on Re-hospitalization in Patients with Sleep-Disordered Breathing with co-morbid COPD.

Confidential

Standard of care: Portable sleep test results will be communicated to the participant and their health care provider. Timing and determination of further evaluation and treatment of the participant's sleep disordered breathing will be per their participant's health care provider's usual care pathway. Sites with change in usual care pathways that involve immediate initiation of PAP therapy as a standard practice will remain in the study. Such data will be analyzed in "per-protocol analysis". Participants in the SOC arm will receive phone calls to promote medication adherence.

Post Discharge Study period (60 days)

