A Pilot, Multi-Center, Randomized, Open-Label, Parallel Group Study to Assess the Effects of a Novel Application of Averaged Volume Assured Pressure Support Ventilation (AVAPS-AE) therapy on Re-hospitalization in Patients with Sleep-Disordered Breathing with co-morbid COPD.

Confidential

intervention and SOC groups will receive \$150.00 as compensation for participating in the study. Compensation will be pro-rated based on completion of study milestones.

Information regarding admission, diagnostic tests, medication changes, and procedures will be collected from all participants. Discharge summaries of re-hospitalizations and office or ER visits and diagnostics tests and therapies received will be collected for measuring healthcare costs.

Participants will be asked if they would be interested enrolling in a registry for a 3 year follow-up. This will involve participants being contacted on a yearly basis inquiring about any hospitalizations, cardiovascular events, and assessment of vital statistics in the National Death Index registry. Participants who elect to enroll the registry will receive an additional \$25 in compensation.

Transition Plan:

Upon completion of the study or earlier termination, site investigators will cooperate with the study participants' primary health care providers regarding continuity of care to assure that participants receive appropriate follow-up care after the conclusion of the study. Study participants who are randomized to the treatment group, where a therapeutic benefit is evident, will be allowed to keep the provided AVAPS device until a similar replacement device can be provided to the participant through usual care pathways as part of this transition plan. Study participants who are randomized to the SOC group will have the option of receiving an AVAPS unit at the end of the 60 day period if prescribed and provided through the usual care pathway of their healthcare provider as part of this transition plan. The risk of additional and on-going device supplies not being covered by insurance or involving co-pays will be explained to the participant within the consent. Philips will not be responsible for providing device maintenance or study supplies after the 60 day study period.

Study Process Flow:

Study Procedures	Hospital Procedures (Pre-Discharge)	Post Discharge Study Procedures	Post 60 Day Study Procedures
Informed consent	X		
Inclusion/Exclusion Review	X		
Medical History Assessment	X		
Vitals	X		

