A Pilot, Multi-Center, Randomized, Open-Label, Parallel Group Study to Assess the Effects of a Novel Application of Averaged Volume Assured Pressure Support Ventilation (AVAPS-AE) therapy on Re-hospitalization in Patients with Sleep-Disordered Breathing with co-morbid COPD.

Confidential

Physical Exam	X		
Medication Assessment	X		
Bedside Spirometry	X		
Room Air SpO2 assesment	X		
Anthropometric measurements	X		
Stop -Bang Questionnaire	X		
20 minute PAP Wash-in	X		
QOL questionnaires (FOSQ and SF-36)	X	X	X
Charleston Co-Morbidity Index	X		
Overnight Portable Sleep Test	X		
Randomization	X		
Device Set up training/Mask fitting	X		
1 week PAP adherence assessment (Treatment Group only)		X	
Weekly phone calls to promote PAP and medication adherence		X	
30 day Healthcare utilization assessment and questionnaire Phone Call		X	
60 day Healthcare utilization assessment and questionnaire Phone call		X	
Transition Plan			X
Optional Registry			X

VII. Statistical Analysis

The method described by Cook and Lawless will be used to handle repeated hospitalizations, physician office visits, or emergency room visits in patients who may or may not also have a terminal event. All repeated hospitalizations that occur in patients will be counted. We will use the count-approach and the gap-time approach, described by Cook and Lawless because we are interested in studying event occurrence rates in the two groups as well as the time to occurrence of events. Analysis will be performed for both 30- and 60-days. Actuarial costs will be assessed in patients belonging to both the intervention and usual care arm. Unadjusted comparisons of these costs will be made by independent t-tests or non-parametric equivalent. Differences will be adjusted for potential confounders and other covariates in

A Pilot, Multi-Center, Randomized, Open-Label, Parallel Group Study to Assess the Effects of a Novel Application of Averaged Volume Assured Pressure Support Ventilation (AVAPS-AE) therapy on Re-hospitalization in Patients with Sleep-Disordered Breathing with co-morbid COPD.

Confidential

multivariate regression models, to include age, gender, race, body mass index, baseline severity of COPD, AVAPS-AE and medication adherence. Biologically plausible effect modification will be evaluated before significant confounders are selected by inspection of significance levels as well as impact of estimated coefficient for hypothesis variable.

Data and Safety Monitoring Plan:

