This clinical study will be monitored by Philips Respiromics Inc. (Sponsor) in compliance with the Code of Federal Regulations (CFR) for clinical research; namely, 21 CFR Parts 50, 54, 56 and 812 and others as applicable. The purpose of such monitoring is to assure that the study remains in compliance with the approved protocol, investigator agreement and regulatory requirements, and to resolve any issues that arise during the conduct of the study. The monitoring process includes initial site qualification, periodic visits to the site, and a final visit to the site once the study is complete. Monitoring visits are scheduled periodically throughout the conduct of the study to assure compliance with the investigational plan, and to verify the completeness and accuracy of study data. Monitoring also aids in identifying any research-related problems for the sponsor and/or investigator to correct. The Sponsor will conduct monitoring visits with appropriately trained clinical research professionals.

X. Confidentiality

Confidentiality of participant identification and test-related information is very important. The privacy rules and requirements according to governing regulations will be implemented. Methods to protect the privacy of participants and clinical information will be used. A unique identification number designed to protect the identity of participants will be used to identify the participant on report forms, recruitment logs, data forms or other reports containing information or referring to a participant.

A Pilot, Multi-Center, Randomized, Open-Label, Parallel Group Study to Assess the Effects of a Novel Application of Averaged Volume Assured Pressure Support Ventilation (AVAPS-AE) therapy on Re-hospitalization in Patients with Sleep-Disordered Breathing with co-morbid COPD.

Confidential

X. References

1. Trends in Chronic bronchitis and emphysema. Morbidity and Mortality. . Part II ALA Epidemiological and Statistics unit Research and Program Services. May 2005.
2. Trends in Chronic bronchitis and emphysema. Morbidity and Mortality. Part II. ALA Epidemiological and Statistics unit. Research and Program Services. 2005 May.
3. <http://www.lung.org/lung-disease/copd/resources/facts-figures/COPD-Fact-Sheet.html#Sources>. 2013;Last accessed March 12, 2014.

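### The unadjusted cost comparison may use a rank test, which does not compare mean costs, and the plan does not say whether the AVAPS-AE device is costed

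*Combined protocol and SAP*

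**What the plan says.** Healthcare costs head the list of secondary endpoints in Section III, and the second specific aim in that section refers to "costs related to re-hospitalization; number of visits to physician offices or emergency rooms". Section VII states: "Actuarial costs will be assessed in patients belonging to both the intervention and usual care arm". The next sentence gives the method: "Unadjusted comparisons of these costs will be made by independent t-tests or non-parametric equivalent". The non-parametric method is not named, nothing says when it replaces the t-test, and no target quantity such as a difference in means is stated. The section then adjusts the differences by regression on demographic and baseline variables and on AVAPS-AE and medication adherence. It gives no model family or link.

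On cost inputs, Section VI (Day 60) says: "Discharge summaries of re-hospitalizations and office or ER visits and diagnostics tests and therapies received will be collected for measuring healthcare costs". On the device, Section VI (Intervention Group) says: "Participants in the intervention group will be sent home the AVAPS-AE therapy device". The Transition Plan in Section VI adds: "Philips will not be responsible for providing device maintenance or study supplies after the 60 day study period"; Section IX identifies that company as the sponsor. No section gives unit prices or a costing perspective, or says whether the device, mask, supplies and set-up are charged to the intervention arm.

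**The concern.** Readmission costs will be zero for most participants and large for a few. A statistician who sees such data may well take the non-parametric option, and the usual choice is the rank-sum test. With many ties at zero, that test responds mainly to how many participants had any cost. It does not test the difference in mean cost per participant, which is what determines total expenditure. If one arm has fewer but dearer events, a significant result can appear when the means are equal, or can point the wrong way.

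The device question is separate. Every intervention participant receives a device, so including or excluding it shifts that arm's mean by the full device cost. If the plan leaves this open, the sign of the cost difference may depend on a decision taken after the data are seen.

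**Working it through.** **The plan's own figure.** Section V plans 60 completers with 25% attrition: 60 / (1 - 0.25) = 80, which matches the stated enrolment. There is no power calculation for cost. The allocation ratio is not written; assuming 1:1, the arms have 30 completers or 40 enrolled. At the 20.5% 30-day readmission rate in the section on risks, that is 30 x 0.205 = 6.15 to 40 x 0.205 = 8.2 expected readmissions per arm.

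**Rank test against mean cost.** Assumptions not in the documents: two-sided 5% level; cost zero without an event, otherwise lognormal with log SD 1; the event rates and amounts shown. Each scenario was simulated at least 4,000 times. Mean cost per patient = event rate x mean cost per event.

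| SOC against AVAPS-AE | True means | Rank test rejects, 30 per arm | Rank test rejects, 40 per arm |
|---|---|---|---|
| 35% x 10k against 20% x 17.5k | 3.5k, 3.5k | about 18% to 19% | 24% to 26% |
| Same, plus assumed 1k background cost for everyone | 4.5k, 4.5k | about 13% to 15% (range over both sizes) | see left |
| 35% x 10k against 30% x 11.7k (mild trade-off) | 3.5k, 3.5k | not tabulated | about 5% to 7% |
| 20% x 20k against 40% x 10k (pattern reversed) | 4k, 4k | about 29%, against AVAPS-AE | about 36% to 38%, against AVAPS-AE |
| 40% x 10k against 20% x 25k | 4k, 5k | about 27% to 28%, for AVAPS-AE | about 34%, for AVAPS-AE |

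Welch's test rejects in about 5% of trials in the first scenario.

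A second set of runs used the protocol's own rate, with cost in units of one readmission and an assumed coefficient of variation of 1. It compared 20.5% x 1 with 10.25% x 2, so both means are 0.205. The rank test declared the arm with fewer events cheaper in 16.5% of trials at 30 per arm and 21.1% at 40, against a nominal 2.5% in that direction. Welch's test did so in 5.5%, so it is not exact with data this skewed, but it is much closer.

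**Device break-even.** Saving per patient, in units of one readmission = baseline rate x relative reduction:

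- 10% reduction: 0.205 x 0.10 = 0.0205
- 25% reduction: 0.205 x 0.25 = 0.051
- 50% reduction: 0.205 x 0.50 = 0.1025

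A device cost above that fraction of one readmission's cost, net of any sleep testing or PAP cost in the SOC arm, turns an apparent saving into a loss. For example, with halved readmissions and a device costing 0.20 of a readmission, the difference is -0.1025 without the device and -0.1025 + 0.20 = +0.0975 with it. The 20.5% rate is for 30 days and the study period is 60. At an assumed rate of 40% the three thresholds become 0.04, 0.10 and 0.20.

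**Charging the device but keeping the rank test.** Take halved readmissions from 20.5%, no other costs, and a device costing 0.02 of a readmission. The true difference is 0.1025 + 0.02 - 0.205 = -0.0825, so AVAPS-AE is cheaper. The rank test nevertheless declares it dearer in 99.0% of trials at 30 per arm, because every intervention patient then outranks all the zero-cost controls. With the rate halved from an assumed 40%, the figure is 51% at 30 per arm and 62% at 40. The effect depends on a block of zero-cost controls: a rerun at 20.5% with a readmission at 10k, the device at 0.2k and the same 1k background cost brought it below 10%.

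**The case against.** The case for leaving the text alone has real substance:

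- The t-test is listed first and does compare means. The alternative is unnamed, and a bootstrap or permutation test of means would fit the words. This stands: the rank test is the usual reading, not a stated choice.
- The quoted sentence covers only the unadjusted comparison, and regression follows. This stands in part. The regression may target means, but its family is not stated and it conditions on adherence, which is measured after randomisation. It is not a clear rescue.
- The large rejection rates need an assumed pattern of fewer but much dearer events, which nothing in the documents predicts. Costs also include office visits, tests and therapies, so total cost may not be mostly zero. Both points stand and are reflected in the lower rows of the table.
- The item on therapies in "diagnostics tests and therapies received will be collected for measuring healthcare costs" could include the device. If cost means only re-hospitalisation cost, as one phrase of the second aim suggests, leaving the device out is a choice of scope that needs labelling, not an error. This stands.

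A reader might infer that the rank test and the device question both push towards a false saving for AVAPS-AE. The calculations do not support this: the rank test favours whichever arm has fewer patients with cost, and it can turn against AVAPS-AE once the device is charged. A reader might also infer that the device generates no charge while SOC sleep care is billed to insurance. The documents describe study provision and usual-care pathways, but not billing during the 60 days.

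**Conclusion.** The concern holds as two linked gaps in specification. First, the plan permits a test that, on its usual reading, does not address mean cost. Where the arms differ in both event frequency and cost per event, it can reject equal means about 18% to 26% of the time at the planned sizes, against about 5% for Welch's test. The figure is about 13% to 15% with a modest background cost and near nominal under a mild trade-off. Second, the plan does not say whether the device is costed. At 20.5%, a device cost of about 10% of one readmission would cancel the saving from halving readmissions.

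These sizes rest on assumed cost distributions, event patterns, 1:1 allocation and a 5% level; neither a readmission price nor a device price is in the documents. The documents do not show that the plan is tilted towards AVAPS-AE, that a rank test will be used, or that the device is excluded. Cost is one of six secondary endpoints in a pilot with about 6 to 8 expected 30-day readmissions per arm, and the primary endpoint is unaffected. Severity is minor to moderate.

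**What to change.** Before the data are examined, amend Section VII as follows:

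- Make the difference in arithmetic mean cost per randomised participant the estimand, and define what actuarial cost covers and from whose perspective.
- Estimate it with a bootstrap 95% confidence interval, or with a log-link GLM with robust standard errors adjusted for baseline covariates only. Take adherence out of that model, and delete the non-parametric alternative.
- Apply one stated unit-price table to both arms: device, mask and set-up in the intervention arm; sleep testing and any PAP in the SOC arm.
- Report the difference with and without device cost.

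Make these changes together. Charging the device while keeping a rank test could make AVAPS-AE look dearer in almost every trial if most controls have zero cost, even when its true mean is lower.

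The cost is some protocol or SAP wording, a price table and a little more analysis. No extra participants, visits or clinical changes are needed. The drawback is that the cost figure may look less favourable to the intervention, and with so few readmissions the interval will be wide.

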- One week Device Adherence Assessment (Intervention Group)

During the first 2-7 business days post discharge, research staff will evaluate participant's device adherence via remote download. Participants with poor adherence to AVAPS-AE at home (adequate adherence defined as \geq 4 hours of use on at least 5 of the first 7 nights) will not be included in the "per-protocol analysis" (Such participants will, however, be considered in the intention to treat analysis). Per the investigators discretion, the device setting parameters may be adjusted at this time.

- Weekly Phone Follow-ups (Initial 30 days only):

Phone calls will be made weekly (\pm 2 business days) by the study coordinator to assess mask interface issues (Intervention group) and encourage adherence to AVAPS-AE (Intervention group) and medications (both intervention and SOC group). If participants require an additional visit related to issues noted above, this visit may occur either in the home or as an office to the study site.

- Day 30

At 30 days (\pm 2 business days) post discharge, participants in both Intervention and SOC groups will receive a phone call to determine if they had been admitted to this hospital, or had an unplanned visit to a physician's office or emergency room. Participants will be asked to complete FOSQ and SF-36 questionnaires. Participants will be given the option of completing the questionnaires verbally via phone call or completing handwritten copies and returned via direct mail. Postage paid return envelopes will be provided to participants who elect to complete and return the surveys by mail.

- Day 60

On day 60 (\pm 2 business days), participants in both Intervention and SOC groups will receive a phone call to determine if they had been admitted to this hospital, or had an unplanned visit to a physician's office or emergency room. Participants will be asked to complete a final FOSQ and SF-36 questionnaire. Participants will be given the option of completing the questionnaires verbally via phone call or completing handwritten copies and returned via direct mail. Postage paid return envelopes will be provided to participants who elect to complete and return the surveys by mail. Participants in both

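### The adjusted cost comparison lists adherence as a covariate without coding or timing, so its arm coefficient need not be the intention-to-treat difference

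*Combined protocol and SAP*

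**What the plan says.** Section VII (Statistical Analysis) deals with costs in three consecutive sentences. Costs will be assessed in both arms. "Unadjusted comparisons of these costs will be made by independent t-tests or non-parametric equivalent". Differences are then to be adjusted in "multivariate regression models, to include age, gender, race, body mass index, baseline severity of COPD, AVAPS-AE and medication adherence". The adjustment sentence names no outcome. The nearest antecedent is cost, which is secondary endpoint 1 in Section III, and the text does not clearly extend the adjustment to the primary event analysis. The section then has confounders chosen by their significance levels and by how far they move the coefficient of interest.

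The protocol says this about adherence elsewhere:

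- **Device.** Section VI defines adequate use as at least "4 hours of use on at least 5 of the first 7 nights", read by remote download after discharge. Its stated purpose is to define the per-protocol set; of poor adherers it says "Such participants will, however, be considered in the intention to treat analysis". The Study Process Flow lists "1 week PAP adherence assessment (Treatment Group only".
- **Medication.** The weekly calls are to "encourage adherence to AVAPS-AE (Intervention group) and medications (both intervention and SOC group", and the flow table lists "Weekly phone calls to promote PAP and medication adherence". No measure, scale or time point is given. The only pre-discharge medication item is a "Medication Assessment".

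**The concern.** The end of the covariate list can be read in two ways.

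- **Reading A:** adherence to the device and adherence to medication. The flow table's parallel phrase about PAP and medication supports this.
- **Reading B:** AVAPS-AE is the arm term, and only medication adherence is a covariate.

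On Reading A, the model conditions on something that happens after randomisation, has no counterpart in the standard-of-care (SOC) arm, and carries part of the device's effect. The adjusted result could then hide a benefit that works through use, or show a false excess cost for the device if sicker patients use it less. On Reading B the covariate is probably also measured after randomisation, because medication adherence is mentioned only with post-discharge calls, but that is an inference.

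On either reading, the same data can give different arm effects depending on coding and timing that the plan does not fix. It also does not say whether the unadjusted or the adjusted comparison counts.

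**Working it through.** **Inputs.** From the protocol: 60 completers from up to 80 enrolled at 25% attrition (Section V); randomisation before discharge (Section II); device adherence assessed after discharge in one arm (Section VI). The protocol gives no cost SD, effect size, adherence rate, correlation, allocation ratio or alpha. These are assumed below: 1:1 allocation, 30 per arm, cost in SD units, two-sided 5%.

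**The plan's own figure.** 60/(1 − 0.25) = 80, which reproduces the enrolment target. The point does not depend on it.

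**1. What the coefficient estimates (Reading A, yes/no use, SOC = 0).** Let p be the adherent share of the device arm and G the mean cost of its adherent patients minus that of its non-adherent patients. Leaving baseline covariates aside:

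- unadjusted: b_ITT = mean(all device) − mean(SOC)
- adjusted: b_adj = mean(non-adherent device) − mean(SOC) = b_ITT − p × G

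The two agree only if G = 0.

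**2. Effect acting through use.** If a fraction m acts through use, G = b_ITT × m/p, so b_adj = b_ITT × (1 − m). With b_ITT = −0.80 and m = 0, 0.25, 0.5, 1, b_adj = −0.80, −0.60, −0.40, 0.00.

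**3. Precision.** The variance of the arm term is multiplied by (2 − p)/(2(1 − p)), which is 1.21, 1.50 and 2.17 for p = 0.3, 0.5 and 0.7. So even at m = 0, where there is no bias, simulated power falls from 86% to 53–79%.

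**4. Sicker patients using it less, no true effect.** Let r be the correlation between latent use and underlying cost. The bias is −r × φ(z)/(1 − p), where φ(z) is the normal density at the use threshold (0.348, 0.399, 0.348 for the three values of p). At r = −0.4:

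- p = 0.3: 0.4 × 0.348/0.7 = +0.20 SD
- p = 0.5: 0.4 × 0.399/0.5 = +0.32 SD
- p = 0.7: 0.4 × 0.348/0.3 = +0.46 SD

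At r = −0.2 these halve to +0.10, +0.16 and +0.23. At r = 0 there is no bias and false rejection is 5%.

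**5. Simulation (least squares, 20,000 replicates per setting, SOC = 0).**

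| | p = 0.3 | p = 0.5 | p = 0.7 |
|---|---|---|---|
| Power, unadjusted, m = 0.5 | 80.0% | 83.6% | 85.1% |
| Power, adjusted, m = 0.5 | 28.1% | 23.9% | 17.8% |
| False rejection, adjusted, r = −0.2 | 6.5% | 7.9% | 8.9% |
| False rejection, adjusted, r = −0.4 | 10.3% | 17.1% | 21.8% |
| Power, adjusted, m = 0.5, lognormal costs | 40.8% | 34.8% | 25.1% |

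With lognormal costs, unadjusted power at m = 0.5 is 84–87%. With no effect and r of −0.2 to −0.4, the bias is +0.07 to +0.38 SD and false rejection 6.5–25.3%.

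**6. Another coding.** Subtracting the device-arm mean from use, with SOC still zero, returns −0.80 at every m, with false rejection of 4.9–5.7%.

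**7. Reading B.** Let the arm shift medication adherence by s SD, let adherence change cost by b per SD, and let r be its correlation with underlying cost. Then b_adj = b_ITT − (b + r) × s. With b = −0.3:

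- s = 0: −0.80, no bias
- r = 0: −0.80 + 0.3 × 0.2 = −0.74 and −0.80 + 0.3 × 0.4 = −0.68
- r = −0.4: −0.80 + 0.7 × 0.2 = −0.66 and −0.80 + 0.7 × 0.4 = −0.52

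With no true difference, false rejection for s = 0.2 and 0.4 is 5.5% and 7.3% (r = 0), or 9.0% and 20.9% (r = −0.4). If b = 0 it is 4.9–9.5%.

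**8. Reading A under a smaller effect.** Suppose the effect is −0.5 SD in users only and p = 0.3, 0.5, 0.7, 0.8. Then b_ITT = −0.5p = −0.15, −0.25, −0.35, −0.40. With equal prognosis G = −0.5 and b_adj = 0. If adherers would cost 0.5 SD less in any case, G = −1.0 and b_adj = −0.5p + p = +0.15, +0.25, +0.35, +0.40, the opposite sign.

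**The case against.** The strongest reply is that the larger biases need several conditions the protocol does not state: the cost reading of the sentence, Reading A, zero coding for SOC, and either mediation through use or use linked to prognosis. What is certain is narrower: an adherence covariate with no coding or timing. That stands, and it is why the claim is only that the coefficient need not be the intention-to-treat difference.

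The chosen effect is also large. At p = 0.3 and m = 1, a difference of −0.80 implies −0.80/0.3 = −2.67 SD per user. With a true difference of −0.20 and m = 0.5 the estimate still halves to −0.10, but power goes only from 11–12% to about 6%. The power loss quoted therefore belongs to the chosen effect; the halving does not.

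The simulation always keeps adherence and omits the other covariates, whereas the plan selects confounders, so its rejection rates are not those of the planned procedure. That is fair. Yet the selection rule looks at the effect on the arm coefficient, and adherence coded zero in SOC can move that coefficient strongly, so the rule may favour keeping it.

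Zero coding may also misdescribe some SOC patients, because the SOC Group text in Section VI retains sites that start PAP at once as usual care. This limits the illustration. It also shows that the SOC value needs stating.

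Finally, the unadjusted comparison preserves the randomised contrast, and the protocol refers to an intention-to-treat analysis. Both are true and limit the harm, but neither says which cost result counts if the two disagree.

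**Conclusion.** The concern holds. The natural reading of the covariate list puts a post-randomisation variable, assessed in one arm, into the between-arm model, and nothing elsewhere in the protocol supplies a coding that would make this harmless. The algebra in step 1 rests only on yes/no use with SOC set to zero. Every magnitude rests on assumed values. Under them the adjusted estimate can be the full difference, half of it, nothing, or of opposite sign, and false rejection can range from 5% to about 22% (25% with skewed costs). Bias is smaller on Reading B, and absent if the arm does not change medication adherence or if adherence is centred within the device arm.

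On the nearest reading only one secondary endpoint of a pilot is affected, the primary event analysis is not clearly touched, and the unadjusted cost comparison is sound. It should be fixed, but it does not undermine the trial.

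**What to change.** Amend Section VII:

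1. Remove device and medication adherence from the between-arm model and name randomised arm as the treatment term. For example: *Cost differences between the randomised arms will be estimated by intention to treat, adjusted for age, sex, race, BMI and GOLD stage, all fixed in advance; adherence is not a covariate.* GOLD stage is the randomisation stratum (Section VI, Randomization), and the other covariates are already listed.
2. Delete the clause that selects confounders by significance and by effect on the arm coefficient. Keep the planned look at effect modification.
3. As a smaller clarification, state whether the unadjusted or the baseline-adjusted intention-to-treat cost comparison is primary. Either is valid.
4. Report adherence descriptively or within the per-protocol analysis already planned. Note there that randomisation does not protect that comparison, because its adherence criterion applies to the intervention arm only. Note also that the SOC Group text assigns data from sites starting PAP immediately to the same analysis.

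The cost is wording in Section VII. No new data, visits or patients are needed.
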